## 9.2 Period of Observation and Documentation

All AEs reported by the patient or detected by the treating physician / investigator, are routinely being documented in the subject's medical records. For the purpose of this observational trial all AEs that occur after the initiation of i.v. epoprostenol (Veletri®) up to the last visit will also be documented on the pages provided in the CRF. AEs will be assessed by the investigator using no-leading questions or observed during any visit during the whole observation. The patient should be motivated to report any AEs by phone to the investigator occurring between clinical visits.

Each event should be described in detail along with start and stop dates, severity, relationship to the observed product, action taken and outcome.

## 9.3 Reporting of Serious Adverse Events

Once an AE/ adverse drug reaction (ADR) is identified, the prescriber / investigator / study coordinator will complete an AE form within 1 working day of the investigator's/ prescriber's knowledge that will be transferred electronically and/or by fax to the PH Centre Heidelberg and Actelion using the Actelion Global Drug Safety (GDS) contact information:

E-mail: [[contact]](mailto:[contact])

[contact]

The AE / ADR form shall include following information:

- Patient/subject demographics
- Protocol number
- Start and end date of treatment with i.v. epoprostenol (Veletri®)
- Nature of the AE including date of onset, severity, chronicity and treatment (including hospitalization)
- Final diagnosis (if available)
- Action taken with respect to the observed medicinal product
- Relationship to the observed medicinal product in the opinion of the investigator
- Concomitant drug therapy at the time of the adverse event
- Outcome (if available)
- Recovery date (if available)
- In the case of death, the cause and post-mortem findings (if available).

The original SAE-reports and all other reports will be kept by the investigator.

## 10 Statistical Procedures

### 10.1 Sample Size Calculation

A sample of ~15 patients will be included into the observational study to gain insights into and collect data regarding the use, safety and tolerability of a systematic drug management of i.v. epoprostenol treatment (Veletri®).

### 10.2 Analysis Variables

#### Primary Outcome variable:

1. The main parameters are the listing and frequency of safety and tolerability parameters of i.v. epoprostenol (Veletri®).

#### Secondary outcome variables:

2. demography (sex, age, height, weight)
3. vital signs (blood pressure, heart rate)
4. exercise capacity as measured by six minute walking distance
5. N-terminal pro-brain natriuretic peptide (NTproBNP)
6. World Health Organization (WHO) functional class
7. Borg dyspnea score
8. blood gas analysis
9. right heart size and function (presence/absence of pericardial effusion and tricuspid annular plane systolic excursion (TAPSE), right atrial and ventricular area, systolic pulmonary arterial pressure, right ventricular pump function, assessed by echocardiography)
10. haemodynamics (right arterial pressure (RAP); mean pulmonary arterial pressure (mPAP); cardiac output (CO), cardiac index (CI); pulmonary vascular resistance (PVR); PVR index (PVRI); pulmonary capillary wedge pressure (PCWP) assessed by right heart catheterisation)
11. symptoms of PAH
12. outcome (survival, transplant-free survival)

According to the current guidelines, patients will be seen in the expert center about every three months. This will allow to collect data within the first 6 months of treatment and compare changes between baseline, 3 and 6 months (~24 weeks).

### 10.3 Definition of Trial Population to be Analyzed

In this open label, multicenter non-interventional, observational study patients with PAH will receive medically indicated i.v. epoprostenol (Veletri®) according to a systematic drug management including initiation, administration, storage, handling of the infusion system and

patient education. Patients in need of treatment escalation according to the current guidelines receiving at least dual oral combination treatment with two PAH-targeted drugs and having an unsatisfying long-term clinical response or are still in an intermediate or high risk group will be eligible for the study.

## **10.4 Statistical Methods**

### **10.4.1 General**

#### **Descriptive statistics**

All data (demographic and other baseline characteristics, continuous data at each routine visit and their change to baseline) will be listed and trial summary tables will be provided. Data of all centres will be pooled.

Descriptive statistics will be displayed, including the usual location and scale statistics (mean, median, standard deviation, standard error, first and third quartiles, minimum and maximum) and 95% confidence limits of mean and median.

Frequency tables for qualitative data will be provided.

If not mentioned otherwise, all statistical tests will be performed with a type I two-sided error rate of  $\alpha=0.05$

#### **Primary endpoint**

The main parameters are safety and tolerability parameters of i.v. epoprostenol (Veletri®). Data regarding safety and tolerability will be collected by listings of adverse reactions during the course of the medically indicated treatment.

**Secondary efficacy variables** will be formally tested for statistical significance of a difference between baseline and 3 months; baseline and 6 months, respectively.

Secondary efficacy analysis comprises hemodynamics, echocardiography, lung function tests, 6MWD, Borg Dyspnea index, Modified Rodnan Skin Score, laboratory parameters, quality of life and safety parameters.

WHO functional class is supposed to either remain the same, improve by one or two categories, or deteriorate by one category in most cases. A change score (baseline minus end of study) will be calculated, which could go from -3 (class 4 at baseline and class 1 at end of study) to +1 (class 3 at baseline and class 4 at end of study). This will be analyzed using the Wilcoxon test.

#### **Safety analysis**

All tabulations will be descriptive only. Tables will be produced for adverse events and serious adverse events.

Mortality in the 6 month period of the study will be summarized descriptively. Any deaths in the study period will be listed, with day of death relative to start and stop of study drug and cause of death. Vital signs will be summarized by visit and treatment group.

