## 2 Introduction

### 2.1 Scientific Background

Chronic pulmonary hypertension (PH) is associated with impaired exercise capacity, quality of life and right ventricular function.[1] The disease is characterized by an increase of pulmonary vascular resistance and pulmonary arterial pressure, leading to right heart insufficiency.[1, 2] Within the last decade, new disease-targeted medical therapies have been approved for treatment of pulmonary arterial hypertension (PAH).[3] Combinations of these agents have shown to further improve symptoms, 6-minute walking distance (6-MWD) and hemodynamics in PAH patients.[1, 3]

The loss of endogenous prostacyclin plays an important role in the pathogenesis of PAH. Prostacyclin has vasodilatory, anti-proliferative, anti-inflammatory and anti-thrombotic properties and is therefore an important target substance in PAH-specific therapy.[4] Epoprostenol was the first specific therapy approved for the treatment of PAH, after showing a positive effect on survival in otherwise treatment naïve patients.[5] Epoprostenol is chemically unstable with a short biological half-life of 3-5 minutes, and must be continuously administered by intravenous (i.v.) infusion using an external pump and in-dwelling central venous catheter. The application of epoprostenol is therefore aggravated by its handling, which makes it a challenge for the patient to store and administer the medication.

Flolan® was the first epoprostenol drug that was made available for treatment of pulmonary arterial hypertension. Reconstituted flolan solution is stable at 2 - 8 °C for up to 48 hours. If used immediately, reconstituted flolan is stable for up to 12 hours at room temperature (< 25 °C), or prior to use at room temperature, reconstituted flolan may be stored at 2 - 8 °C for up to 40 hours. In this case, flolan should not be infused for over 8 hours at room temperature.

With Veletri® an improved epoprostenol solution has been therefore developed to facilitate storage and administration of the drug. It provides a better stability upon reconstitution is self-preserving, does not allow the growth of micro-organisms and allows reconstitution with readily available diluents.

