### 8.1.10 Clinical laboratory data

As available and determined locally on-site, following clinical laboratory data will be collected:

Hematology	Leucocytes, erythrocytes, hemoglobin, hematocrit, platelets
Substrates	Bilirubin, LDL/HDL, cholesterol, triglycerides, creatinine, uric acid, urea, total protein, albumin, glucose
Electrolytes	Sodium, potassium, calcium, chloride
Enzymes	SGOT/ASAT, SGPT/ALAT, Gamma-GT, GLDH, AP, LDH, CK
Others	INR, PTT, $\beta$ -HCG test for women with childbearing potential at initial screening, Visit 3 and Visit 4
Biomarkers	CRP, NT-proBNP

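### Section 10.4.1 files routine laboratory values and safety parameters under formally tested secondary efficacy, against 3.2, 10.2 and its own Safety analysis, which has no laboratory summary

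*Protocol*

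**What the plan says.** Four parts of the protocol bear on where laboratory and safety data belong.

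- **Effectiveness variables (3.2 and 10.2).** NT-proBNP is the only analyte from the 8.1.10 laboratory panel in either list. Blood gases are a separate item. Haematology, coagulation, electrolytes, enzymes and the other chemistry values are absent.
- **Primary outcome (10.2).** This is the listing and frequency of safety and tolerability parameters.
- **Secondary efficacy paragraph (10.4.1, under Primary endpoint).** Efficacy variables are to be tested for change from baseline to 3 months and to 6 months. The list ends with "laboratory parameters, quality of life and safety parameters". The section also sets the level: "all statistical tests will be performed with a type I two-sided error rate of" 0.05.
- **Safety analysis (10.4.1).** All tabulations are descriptive. "Tables will be produced for adverse events and serious adverse events"; mortality, a listing of deaths and vital signs follow. Laboratory values are not mentioned.

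On the data themselves, 8.1.10 states: "As available and determined locally on-site, following clinical laboratory data will be collected". The panel includes platelets, INR, PTT, bilirubin, transaminases and creatinine. Section 10.4.1 adds: "Data of all centres will be pooled".

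**The concern.** The sections disagree on the role of two groups of data. Safety parameters are primary in 10.2 and descriptive in the Safety analysis, yet the efficacy paragraph makes them secondary and tested. The routine laboratory panel is not an effectiveness outcome in 3.2 or 10.2, yet the same paragraph makes it one.

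The background says: "Prostacyclin has vasodilatory, anti-proliferative, anti-inflammatory and anti-thrombotic properties". On that description, a change in platelets, INR or PTT is more naturally read as a safety matter than as effectiveness.

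Two things are at stake. A report that follows the efficacy paragraph would carry many tests labelled efficacy on variables never named as effectiveness outcomes, and some would be significant by chance. Meanwhile the primary safety section would hold no systematic summary of laboratory values that have already been collected. An analysis plan written to this text would inherit the misclassification.

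**Working it through.** The only design figure is the sample size: "A sample of ~15 patients will be included into the observational study". No effect size, standard deviation or power accompanies it, so there is nothing to reproduce. The checks below take n = 15, two-sided alpha = 0.05 and two comparisons per variable from 10.1 and 10.4.1.

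**1. Number of tests implied by a literal reading.** Count of analytes in 8.1.10, leaving out the pregnancy test:

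- haematology 5
- substrates 11 (LDL and HDL counted separately)
- electrolytes 4
- enzymes 7
- coagulation 2
- biomarkers 2 (CRP, NT-proBNP)

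Total: 5 + 11 + 4 + 7 + 2 + 2 = 31.

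Tests: 31 × 2 = 62. Expected false positives if nothing changes: 62 × 0.05 = 3.1. This expectation does not need independence.

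Chance of at least one false positive if the tests were independent: 1 − 0.95^62 = 0.958. Correlation between analytes would lower this figure.

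Without NT-proBNP, which is a named effectiveness variable, 30 × 2 = 60 tests remain, with 60 × 0.05 = 3.0 expected false positives.

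**2. What a group test does with one affected patient.** The protocol names no test for laboratory values, so a one-sample t test on change scores is assumed. Let one patient change by D and the other 14 not at all.

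- Mean change = D/15, which is 6.7% of D.
- Standard deviation = |D|/√15.
- Standard error = (|D|/√15)/√15 = |D|/15.
- |t| = (|D|/15)/(|D|/15) = 1.00 on 14 degrees of freedom, so p = 0.33 whatever the size of D.
- Median and both quartiles = 0. The minimum (or maximum) = D.

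With random variation added to all 15 patients (assumed SD of 0.1, 0.25, 0.5 and 1.0 times D; 100,000 simulated data sets each), the test rejects in 0.2%, 3.5%, 4.8% and 5.0% of runs. It does no better than its nominal 5% level.

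**3. What an individual count would report.** If that patient moved outside the local reference range, a count gives 1/15 = 6.7% (exact 95% interval 0.2% to 31.9%). The condition matters: a large change that stays within range would not be counted.

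**The case against.** The strongest reply is that laboratory harm already has a route to the primary safety result. Section 9.1.1 defines an adverse event so that it includes an abnormal laboratory finding. Section 9.2 has all events after initiation recorded in the CRF, 9.1.5 grades them by CTCAE v4.03, and the Safety analysis tabulates them. This stands. A reader might infer that a laboratory harm is averaged away from the primary safety answer, or that only changes the site calls significant count as events. The documents support neither: the significant-change wording in 9.1.1 is an example, and the definition is wider.

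Nor would an extreme value be invisible. Section 10.4.1 lists all data with change from baseline and reports minimum and maximum. With about 15 patients, a listing shows every value, although the planned statistics do not say whether it was outside the local range.

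A reader might also infer that values from different laboratories are pooled raw. The protocol says only that centres are pooled. It is silent on units and reference ranges, and the CRF is not shown.

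Shift tables and range handling are often left to an analysis plan, so their absence alone would be no finding. The efficacy list also looks like loose drafting, since it contains other items that are not in 10.2. But the misplacement is stated in the protocol, and loose drafting does not remove the conflict.

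What remains is that the adverse-event route depends on the investigator recognising and reporting the finding. Section 8.1.9 says ECG data will be reviewed for potential adverse events; 8.1.10 says nothing comparable for laboratory data.

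**Conclusion.** The point holds as a misclassification within section 10.4.1 that conflicts with 3.2, 10.2 and the Safety analysis. Its size is up to 62 tests labelled efficacy, about 3.1 of them expected to be falsely positive if nothing changes. Group testing has no useful ability to show a single-patient abnormality (p = 0.33 in the simplest case).

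The 62 assumes that every analyte is tested at both times. Data are collected only as available, so the real number could be smaller. The p-value assumes a t test, 15 complete pairs and one affected patient.

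The conclusion does not extend to harms being lost: reported abnormalities reach the primary tables, and extremes remain in the listings and range. The gap is a systematic descriptive laboratory summary within the primary safety analysis. In a descriptive study of about 15 patients this is moderate. It should be corrected because it touches the primary objective and is cheap to put right.

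**What to change.** In 10.4.1:

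- In the secondary efficacy list, replace laboratory parameters with NT-proBNP and delete safety parameters. Blood gases keep their own place in 10.2; if the general term was meant to cover them, name them.
- In the Safety analysis, add: For each haematology, coagulation and chemistry value (including CRP), a descriptive table will give the number of patients below, within and above the local reference range at initiation against the worst value under treatment. No test will be performed.
- Record the local reference range beside each value, if the CRF does not already do so.

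The cost is one more table and a little data entry. No new assessment or test is needed, and up to 60 tests labelled efficacy disappear (62 less the two for NT-proBNP).

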## **11 Data Management**

### **11.1 Data Collection**

A paper-based case report form (CRF) will be used in this study. All entries made in the CRF must be verifiable against source documents.

All findings including clinical and laboratory data will be documented in the subject's medical record and in the CRF. The investigator is responsible for ensuring that all sections of the CRF are completed correctly and that entries can be verified against source data. Any errors should have a single line drawn through them so that the original entry remains legible. The correct data should be entered at the site with the investigator's signature, date and reason for change to confirm the correctness of entries in the CRF. Self-explanatory corrections need not to be justified.

The correctness of entries in CRF will be confirmed by dated signature of the responsible investigator. The original CRF will be transferred to the data management, one copy will be kept by the investigator.

### **11.2 Data Handling**

After first check for plausibility by eye, all data will be entered in a database as recorded in the CRF. After completion of data entry, checks for plausibility, consistency, and completeness of the data will be performed. Based on these checks, queries will be produced combined with the queries generated by visual control.

All missing data or inconsistencies will be reported back to the centre and clarified by the responsible investigator. If no further corrections are to be made in the database it will be declared closed and used for statistical analysis.

### **11.3 Storage and Archiving of Data**

According to the Joint Recommendations of BfArM and PEI on planning, execution and evaluation of observational trials (current version from 7th July 2010) all important trial documents (e.g. CRF) will be archived for at least 10 years after the termination of the observation.

## **12 Ethical and Legal Aspects**

### **12.1 Good Clinical Practice**

The procedures set out in this observational protocol, pertaining to the conduct, evaluation, and documentation of this observational trial, are designed to ensure that all persons involved in the trial abide by Good Clinical Practice (GCP) and the ethical principles described in the applicable version of the Declaration of Helsinki. The trial will be carried out in keeping with local legal and regulatory requirements.

### **12.2 Subject Information and Informed Consent**

Before being admitted to this observational trial, the subject must consent to participate after the nature and scope of the observation have been explained in a form understandable to him or her. The subject must give consent in writing. The signed Informed Consent Form will be filed by the investigator.

A copy of the signed informed consent document must be given to the subject. The documents must be in a language understandable to the subject and must specify who informed the subject.

The subjects will be informed as soon as possible if new information may influence his/her decision to participate in the trial. The communication of this information should be documented. Patients will be informed of the right to refuse to participate in the trial or to withdraw consent to participate at any time without reprisal. Upon request, already collected data can be deleted.

### **12.3 Confidentiality**

The data obtained in the course of the trial will be treated pursuant to relevant European and national legal requirements on data protection

During the observational trial, subjects will be identified solely by year of birth and an individual identification code (subject number, randomization number). Trial findings stored on a computer will be stored in accordance with relevant European and national legal requirements on data protection and will be handled in strictest confidence. For protection of these data, organizational procedures are implemented to prevent distribution of data to unauthorized persons. The appropriate regulations of local data legislation will be fulfilled in its entirety.

The subject consents in writing to release the investigator from his/her professional discretion in so far as to allow inspection of original data for monitoring purposes by health authorities and authorized persons (inspectors, monitors, auditors). Authorized persons (clinical monitors, auditors, inspectors) may inspect the subject-related data collected during the trial.

The investigator will maintain a subject identification list (subject numbers with the corresponding subject names) to enable records to be identified.

Subjects who did not consent to circulate their pseudonymized data will not be included into the observational trial.

#### **12.4 Responsibilities of the Investigator**

The investigator should ensure that all persons assisting with the observational trial are adequately informed about the protocol, any amendments to the protocol and their trial-related duties and functions.

The investigator should maintain a list of subinvestigators and other appropriately qualified persons to whom he or she has delegated significant trial-related duties.

#### **12.5 Approval of Trial Protocol and Amendments**

Before the start of the observational trial, the trial protocol, informed consent document, and any other appropriate documents will be submitted to the independent Ethics Committee (EC) and the trial will as well be reported to the competent higher federal authority (BfArM), the Federal Association of Panel Doctors, the Central Federal Association of the health insurance funds, as well as the Association of Private Health Insurance Funds. A written favorable vote of the EC is a prerequisite for initiation of this trial. The statement of EC should contain the title of the trial, the trial code, the trial site, and a list of reviewed documents. It must mention the date on which the decision was made and must be officially signed by a committee member. This documentation must also include a list of members of the EC present on the applicable EC meeting and a GCP compliance statement.

Before the first subject is enrolled in the trial, all ethical and legal requirements must be met. All planned substantial changes will be submitted in writing as protocol amendments to EC and the relevant authorities mentioned above.

The investigator will keep a record of all communication with the EC and the relevant authorities.

#### **12.6 Information to Independent Ethics Committee**

The EC and the regulatory authorities must be informed of the end of the trial within one year following the completion of the data collection process.

#### **12.7 Notification of Regulatory Authorities**

The local regulatory authorities responsible for each particular investigator will be informed before the beginning and at the end of the trial according to the applicable regulations. Each investigator is obliged to notify his/ her local regulatory authority.

